8.3. Vital Sign Measurements

Vital signs (SBP and DBP, oral body temperature, respiratory rate, and HR) will be collected at Screening, Check-in Day -3, before dosing (30 to 60 minutes prior to the initiation of the study

drug infusion), and at 10, 20, 30, 45, 60 minutes, 24 and 48 hours following initiation of the study drug, and on Days 7 and 28 (± 2).

Vital signs results will be presented in a data listing sorted by treatment group, subject, and collection date/time. Actual results and change from baseline will be summarized for the safety population.

All vital sign tables and listings will be provided by Part.

8.4. Twelve-Lead Electrocardiogram

Twelve-lead ECGs will be obtained after the subject has rested in the supine position for ≥ 10 minutes or as clinically indicated based on reported AEs or laboratory findings, as necessary. Scheduled visit and timepoints for 12-lead ECG will be specified on the Dosing Memo.

Electrocardiogram assessments will include comments concerning whether the tracings are normal or abnormal, rhythm, presence of arrhythmia or conduction defects, morphology, and any evidence of MI, or ST-segment, T-Wave, and U-Wave abnormalities. In addition, measurements of these intervals will be reported: HR, PR interval, QRS duration, QT interval, Fridericia-corrected QT interval (QTcF), and RR interval. The investigator will determine whether any of the 12-lead ECG results are CS or NCS.

If both QT and RR intervals are not missing, the Bazett's-corrected QT interval (QTcB) measured in msec will be calculated using below formula, where RR interval is measured in msec:

$$\bullet \quad QT_{CB} = \frac{QT}{\sqrt{RR/1000}}$$

If both QT and RR intervals are not missing but QTcF interval is missing in the database, QTcF measured in msec will be calculated using below formula, where RR interval is measured in msec:

$$\bullet \quad QT_{CF} = \frac{QT}{\sqrt[3]{RR/1000}}$$

Electrocardiogram results will be presented in data listing sorted by treatment group, subject, and date/time of assessment. In addition, subjects with outlying QTcF, and QTcB intervals (absolute value > 500 msec, absolute value > 480 msec, absolute value > 450 msec, or increase from baseline value > 30 or > 60 msec) will be listed in a separate data listing. A summary table will be presented for maximum QTcF and QTcB intervals (including scheduled and unscheduled assessments) meet the outlying criteria using count and percentage.

Actual results and change from baseline will be summarized for the safety population at each timepoint.

All ECG results will be presented in a data listing.

All ECG tables and listings will be provided by Part.

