**EXCLUSION CRITERIA:**

1. Concern the subject may be unable to comply with study procedures and/or follow-up, or, in the opinion of the investigator, the subject is not suitable for entry into the study
2. History of any acute or chronic medical disorder expected to decrease the life expectancy of the subject
3. History or presence of gastrointestinal (GI), hepatic (with the exception of Gilbert's syndrome), or any other condition known to interfere with absorption, distribution, metabolism, or excretion of drugs
4. Significant renal insufficiency, as indicated by estimated glomerular filtration rate (eGFR)  $<30$  mL/min/1.73m^2 according to the Modification of Diet in Renal Disease (MDRD) equation
5. Any CS acute illness, medical/surgical procedure, or trauma within 4 weeks of administration of study drug or any planned surgical procedure that will occur during the study (from Screening through the Day 28 [ $\pm 2$  days] Follow-up visit)
6. Any CS abnormal findings in physical examination, vital signs, laboratory assessments, and ECG parameters identified during Screening or Check-in. Note: abnormal results may be repeated for confirmation immediately after the first out of range measurement. Abnormal vital signs may be repeated twice if needed, immediately after the first abnormal result and/or after the subject has rested for at least 10 minutes.

Specific vital sign exclusionary criteria occurring after 10 minutes of supine rest are any of the following:

- Systolic blood pressure (SBP)  $<100$  or  $>160$  mm Hg
- Diastolic blood pressure (DBP)  $<40$  or  $>95$  mm Hg
- Resting heart rate (HR)  $<50$  or  $>100$  beats per minute (bpm)

Specific exclusionary criteria for ECG parameters at Screening or Check-in include any of the following:

- Prolonged Fridericia-corrected QT interval (QTcF)  $>450$  milliseconds (msec), shortened QTcF  $<340$  msec, or pause  $>3$  seconds, or family history of long QT syndrome

7. Any specific contraindication to Brilinta® as described in the Brilinta® prescribing information and:
  - History of intracranial hemorrhage, active bleeding, or hypersensitivity or allergic reaction to ticagrelor or any component of the product
  - Any history of severe head trauma, intracranial neoplasm, arteriovenous malformation, aneurysm, or proliferative retinopathy
  - Any history of intraocular, retroperitoneal, or spinal bleeding

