### 3.2.2 Exclusion Criteria

Subjects will be excluded from this study if they meet ANY of the following criteria:

1. Concern the subject may be unable to comply with study procedures and/or follow-up, or, in the opinion of the investigator, the subject is not suitable for entry into the study
2. History of any acute or chronic medical disorder expected to decrease the life expectancy of the subject
3. History or presence of gastrointestinal (GI), hepatic (with the exception of Gilbert's syndrome), or any other condition known to interfere with absorption, distribution, metabolism, or excretion of drugs
4. Significant renal insufficiency, as indicated by estimated glomerular filtration rate (eGFR)  $< 30$  mL/min/1.73m^2 according to the Modification of Diet in Renal Disease (MDRD) equation
5. Any clinically significant (CS) acute illness, medical/surgical procedure, or trauma within 4 weeks of administration of study drug or any planned surgical procedure that will occur during the study (from Screening through the Day 28 [ $\pm 2$  days] Follow-up visit).
6. Any CS abnormal findings in physical examination, vital signs, laboratory assessments, and ECG parameters identified during Screening or Check-in. Note: abnormal results may be repeated for confirmation immediately after the first out of range measurement. Abnormal vital signs may be repeated twice if needed, immediately after the first abnormal result and/or after the subject has rested for at least 10 minutes.

Specific vital sign exclusionary criteria occurring after 10 minutes of supine rest are any of the following:

- SBP  $< 100$  or  $> 160$  mm Hg
- DBP  $< 40$  or  $> 95$  mm Hg
- Resting HR  $< 50$  or  $> 100$  beats per minute (bpm)

Specific exclusionary criteria for ECG parameters at Screening or Check-in include any of the following:

- Prolonged Fridericia-corrected QT interval (QTcF)  $> 450$  milliseconds (msec), shortened QTcF  $< 340$  msec, or pause  $> 3$  seconds, or family history of long QT syndrome

7. Any specific contraindication to Brilinta® as described in the Brilinta prescribing information and:
  - History of intracranial hemorrhage, active bleeding, or hypersensitivity or allergic reaction to ticagrelor or any component of the product
  - Any history of severe head trauma, intracranial neoplasm, arteriovenous malformation, aneurysm, or proliferative retinopathy
  - Any history of intraocular, retroperitoneal, or spinal bleeding

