**EXCLUSION CRITERIA:**

1. Concern the subject may be unable to comply with study procedures and/or follow-up, or, in the opinion of the investigator, the subject is not suitable for entry into the study
2. History of any acute or chronic medical disorder expected to decrease the life expectancy of the subject
3. History or presence of gastrointestinal (GI), hepatic (with the exception of Gilbert's syndrome), or any other condition known to interfere with absorption, distribution, metabolism, or excretion of drugs
4. Significant renal insufficiency, as indicated by estimated glomerular filtration rate (eGFR)  $<30$  mL/min/1.73m^2 according to the Modification of Diet in Renal Disease (MDRD) equation
5. Any CS acute illness, medical/surgical procedure, or trauma within 4 weeks of administration of study drug or any planned surgical procedure that will occur during the study (from Screening through the Day 28 [ $\pm 2$  days] Follow-up visit)
6. Any CS abnormal findings in physical examination, vital signs, laboratory assessments, and ECG parameters identified during Screening or Check-in. Note: abnormal results may be repeated for

confirmation immediately after the first out of range measurement. Abnormal vital signs may be repeated twice if needed, immediately after the first abnormal result and/or after the subject has rested for at least 10 minutes.

Specific vital sign exclusionary criteria occurring after 10 minutes of supine rest are any of the following:

- Systolic blood pressure (SBP) <100 or >160 mm Hg
- Diastolic blood pressure (DBP) <40 or >95 mm Hg
- Resting heart rate (HR) <50 or >100 beats per minute (bpm)

Specific exclusionary criteria for ECG parameters at Screening or Check-in include any of the following:

- Prolonged Fridericia-corrected QT interval (QTcF) >450 milliseconds (msec), shortened QTcF <340 msec, or pause >3 seconds, or family history of long QT syndrome

7. Any specific contraindication to Brilinta® as described in the Brilinta® prescribing information and:
  - History of intracranial hemorrhage, active bleeding, or hypersensitivity or allergic reaction to ticagrelor or any component of the product
  - Any history of severe head trauma, intracranial neoplasm, arteriovenous malformation, aneurysm, or proliferative retinopathy
  - Any history of intraocular, retroperitoneal, or spinal bleeding
  - Have taken, within 30 days of Screening, any oral or parenteral anticoagulant, including low molecular-weight heparin

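### The absolute QTc rows in SAP 8.4 (>450, >480, >500 msec) are neither limited to post-dose ECGs nor split by Baseline, so an eligible subject can be a QTcB outlier before any study drug.

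*SAP*

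**What the plan says.** SAP 8.4 derives QTcB from QT and RR, and derives QTcF the same way when it is missing from the database. It sets absolute criteria, "absolute value > 500 msec, absolute value > 480 msec", and continues with "absolute value > 450 msec, or increase from baseline value > 30 or > 60 msec". Subjects meeting any of these are listed separately. The table is then defined: "A summary table will be presented for maximum QTcF and QTcB intervals (including scheduled and unscheduled assessments) meet the outlying criteria". SAP 8.4 also summarises actual values and change from baseline at each timepoint and lists all ECG results.

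SAP Section 4 defines Baseline as the last non-missing value before study drug. It also keeps unscheduled results out of summary tables except for determining Baseline, which SAP 8.4 contradicts for this table.

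On entry, Protocol Section 3.2.2 (Part A) introduces the ECG limits with "Specific exclusionary criteria for ECG parameters at Screening or Check-in include any of the following". The limit, the same in Part A and Part B, is "Prolonged Fridericia-corrected QT interval (QTcF) >450 milliseconds (msec), shortened QTcF <340 msec". The heart-rate limit is "Resting heart rate (HR) <50 or >100 beats per minute (bpm". No eligibility criterion mentions QTcB.

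**The concern.** Read literally, a maximum over all ECGs includes the pre-dose ones. A subject whose highest value came before the infusion is then counted as an outlier under the treatment to which he or she was assigned. Even if the maximum is programmed as post-dose, a subject who was above 450 msec at Baseline and stays there is counted the same way as one who newly crosses the threshold.

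The SAP avoids this elsewhere. An adverse event is treatment-emergent only if it is new or worse after exposure (SAP 8.1). A subject with a positive pre-treatment antibody sample counts as ADA-positive only if a later titer is at least twice as high (SAP Section 9). The absolute QTc rows have no such rule.

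Safety is a primary objective and the groups are small. A cohort of 8 to 12 subjects at 3:1 gives 6 to 9 on PB2452 and 2 to 3 on placebo. One subject counted for a pre-dose value is therefore 1/9 to 1/6 (11-17%) of an active cohort.

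**Working it through.** There is no plan figure to reproduce: neither document states an expected outlier rate, a QTc mean or a QTc SD.

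**1. Which ECGs can supply the maximum.** In the Part B Schedule of Events (footnote f) the scheduled ECGs are Screening, Day -1, Day 1 pre-dose, after bolus, end of infusion, 24 hours, and Days 3, 7 and 28. That is 3 before and 6 after the start of infusion, so 3 of the 9 scheduled ECGs in a literal maximum are pre-dose. Dosing Memos may change the schedule.

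**2. QTcB from QTcF (documents only).** The SAP formulas are QTcB = QT/(RR/1000)^(1/2) and QTcF = QT/(RR/1000)^(1/3), with RR = 60000/HR msec. Dividing gives QTcB = QTcF × (RR/1000)^(-1/6).

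| HR (bpm) | RR (msec) | QTcB/QTcF | QTcF at which QTcB = 450 | QTcB if QTcF = 450 |
|---|---|---|---|---|
| 50 | 1200 | 0.970 | 463.9 | 436.5 |
| 60 | 1000 | 1.000 | 450.0 | 450.0 |
| 75 | 800 | 1.038 | 433.6 | 467.1 |
| 80 | 750 | 1.049 | 428.9 | 472.1 |
| 90 | 667 | 1.070 | 420.6 | 481.5 |
| 100 | 600 | 1.089 | 413.3 | 490.0 |

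Examples inside the entry limits:
- QTcF 430 at 80 bpm: 430 × 1.0491 = 451, in the >450 row.
- QTcF 450 at 90 bpm: 450 × 1.0699 = 481, in the >480 row.

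Both can occur before study drug. Even at the upper heart-rate limit, an eligible QTcF at entry gives a QTcB of at most 490, so the >500 row is not reached this way at entry.

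**3. QTcF at entry.** The lowest absolute row uses the entry cut-off, so the limit removes most pre-existing QTcF cases. It does not remove all of them. It applies at Screening or Check-in, but the Day -3 lists in Protocol Section 3.5 of both Parts name no 12-lead ECG, and no QTcF limit is stated for the Day -1 or pre-dose ECG.

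**4. Illustrative size (assumed values, no drug effect).** Assumptions: mean QTcF 405-420 msec, between-subject SD 16, ECG-to-ECG SD 6-10, HR 66 bpm (SD 9), entry limits applied to one screening ECG, then 2 pre-dose and 6 post-dose ECGs. The two figures in each QTcB pair below hold heart rate fixed within a subject, or let it vary with SD about 5 bpm.

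- Baseline above 450: QTcF 0.2-3.5%, QTcB about 3-12%.
- Maximum over all ECGs above 450: QTcF 1-14%; QTcB 6-30% or 8-34%.
- Post-dose maximum above 450 with Baseline at or below 450: QTcB 3-17% or 5-20%.
- The same, plus a rise above 30 msec: QTcF 0-2%; QTcB about 0.3-6% with varying heart rate.

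The width of these ranges reflects the assumptions.

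**The case against.** The case against acting is substantial. The >30 and >60 msec rows are measured from the last pre-dose value. Change from baseline is summarised at each timepoint, placebo has its own column, and every ECG is listed by subject and time. A reader might infer that a pre-existing high value cannot be told from a drug effect. The documents do not support that, because these outputs allow each outlier to be read against the subject's own pre-dose ECGs.

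High heart rates are also uncommon in supine, rested subjects. At 66 bpm the ratio is (60/66)^(-1/6) = 1.016, so QTcB passes 450 only when QTcF exceeds 450/1.016 = 443. No test, dose decision or stopping rule is tied to the table: the Safety Review Committee judges DLTs by CTCAE. One subject would be 11-17% of an active cohort under any counting rule.

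All of this stands, and it limits the importance of the point. It does not make the absolute rows correct: as written they still count pre-dose and unchanged high values by treatment group.

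A reader might also infer that the lack of a confirmatory ECG is the main fault and that redefining the table cures it. It does not. Entry allows a repeat ("abnormal results may be repeated for confirmation immediately after the first out of range measurement") and the table requires none, but the change below adds no confirmation rule, and single noisy post-dose readings would still count.

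**Conclusion.** The point holds for the absolute rows only. That the maximum is not restricted to post-dose ECGs, and that pre-existing values are not separated, follows from the text of SAP 8.4. That an eligible subject can be in the QTcB >450 row, or the >480 row, before study drug follows from the SAP formulas and the protocol's QTcF and heart-rate limits, with no further assumption. For QTcF the same gap exists but matters much less, because of the entry limit.

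How often it would happen is not known from the documents. The percentages above rest on assumed means, SDs and heart rates, with one set used for ages 18-50 and 50-80 alike. This is a minor improvement to a descriptive table, and nothing else in the plan depends on it.

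**What to change.** In SAP 8.4:

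1. Define the maximum as the highest post-dose value over scheduled and unscheduled ECGs, and state that this is an exception to the rule on unscheduled results in SAP Section 4.
2. For QTcF and QTcB, count each absolute category (>450, >480, >500 msec) only when Baseline was at or below that threshold. Show subjects already above it at Baseline on a separate line.
3. Add a row for a post-dose value above 450 msec together with an increase of more than 30 msec from Baseline.

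The cost is SAP wording and one reprogrammed table. No ECG is added and no data are lost. The small downside is that subjects already above a threshold at Baseline leave the main count for the separate line, where they remain visible.

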8.5. Holter Monitoring (Continuous Twelve-lead Electrocardiogram)

Continuous 12-lead Holter monitor will be placed 2 hours before administration of study drug and will remain in place for 24 hours after the initiation of study drug. The continuous ECG waveform data recorded by the Holter device will be stored for optional exposure-response QTc analysis.

The eCRF collected interpretation from the Holter device will be presented in a data listing, by Part.

8.6. Physical Examination and Physical Measurement

A full physical examination will include assessment of skin, head, ears, eyes, nose, throat, neck, thyroid, lungs, heart, cardiovascular system, abdomen, lymph nodes, and musculoskeletal system/extremities, and will be performed on Screening, at Check-in Day -3, and at Day 28 (± 2).

A brief physical examination will include assessment of skin (including any signs of cutaneous erythema), lungs, cardiovascular system, and abdomen (liver, spleen) and will be performed at Day 3 and Day 7.

Interim physical examinations will be performed at the discretion of the investigator, if necessary, to evaluate AEs or clinical laboratory abnormalities.

Physical exam results will be presenting in a data listing, by Part. Physical measurements will be presented in a separate listing, by Part.

9. Immunogenicity Assessments

Immunogenicity (antibody) samples will be screened for the presence of binding anti-drug antibodies (ADA) at Check-in Day -3, on Days 1, 7, and 28 (± 2). A subject who tests positive for ADAs at the final scheduled visit (Day 28 ± 2 days) will be asked to return for follow-up sampling approximately 3 months after the final visit and approximately every 6 months thereafter until ADAs no longer test positive or until levels return to a predose state.

The ADA result (positive or negative) will be summarized by treatment group and visit using counts and percentages. All ADA results with corresponding titer values will be presented in a data listing. The neutralizing antibody results may be listed and summarized in the clinical study report if the assay is available.

An ADA-positive subject is defined as a subject with at least one ADA-positive sample at any time during the treatment or follow-up observation period. In case of a positive pre-treatment sample, if the titer of at least one post-treatment ADA is elevated at least 2 folds of the titer in pre-treatment sample, this subject is also ADA positive otherwise ADA negative.

All immunogenicity tables and listings will be provided by Part.

10. Pharmacokinetics

All tables and listings for pharmacokinetics will be provided by Part.

10.1. Plasma Pharmacokinetics

The ticagrelor and TAM pharmacokinetic results will be analyzed for all randomized subjects, and the PB2452 results will be analyzed for the PK Population. All summary tables, graphs are listings will be provided by Part.

10.1.1. Plasma Pharmacokinetics Concentration

Throughout this document, the total MEDI2452 (PB2452) includes free MEDI2452 (PB2452), protein-bound MEDI2452 (PB2452), ticagrelor-complexed MEDI2452 (PB2452), and TAM-complexed MEDI2452 (PB2452). The unbound MEDI2452 (PB2452) includes free MEDI2452 (PB2452) and protein-bound MEDI2452 (PB2452). Similarly, total ticagrelor (or TAM) includes free ticagrelor (or TAM), protein bound ticagrelor (or TAM), and MEDI2452 (PB2452)-complexed ticagrelor (or TAM). The unbound ticagrelor (or TAM) includes free ticagrelor (or TAM).

Blood samples for PK analysis of total and unbound PB2452 concentration in plasma will be collected from all subjects at the following time points: before dosing (0 hour) and up to 28 days after initiation of the study drug (PB2452 or placebo) infusion. Collection time points for cohorts were be specified in a Dosing Memo from Sponsor prior to initiation of each cohort, and are provided below.

Collection times relative to the initiation of the study drug (PB2452 or placebo) infusion on Day 1 were: Hour 0 (up to 10 minutes prior to PB2452 infusion), 5 minutes, 0.25, 0.5, 1, 2, 4, 8, 12, 20, 24, 36, 48 hours, and 7 and 28 days post-dose.

Plasma samples for determining total and unbound concentrations of ticagrelor and its active metabolite TAM, will be collected at the following timepoints: before dosing (within 10 minutes prior to the initiation of the study drug infusion [Hour 0]), and up to 28 days following the initiation of PB2452 or placebo infusion on Day 1. Subjects will be administered the 5th ticagrelor dose two hours before the study drug infusion initiation on Day 1.

Specific collection times relative to the initiation of the study drug (PB2452 or placebo) infusion were: Hour 0 (up to 10 minutes prior to PB2452 infusion), 5 minutes, 0.25, 0.5, 1, 2, 4, 8, 12, 20, 24, 36, 48 hours, and 7 and 28 days post-dose.

Concentrations that are below the limit of quantification (BLQ) will be treated as zero for descriptive statistics. Mean BLQ concentrations will be presented as BLQ, and the SD and

coefficient of variation (CV) will be reported as not applicable. Missing concentrations will be excluded from the calculations.

For each analyte, plasma concentration data will be listed by subject and summarized by time point for each dose level using descriptive statistics (number of subjects, arithmetic mean, SD, CV, median, minimum, and maximum). Plasma concentration versus time profiles for each subject will be presented graphically. The mean plasma concentrations versus scheduled time profiles will be presented graphically by dose.

Scatter plots of total and unbound plasma ticagrelor and TAM versus total and unbound PB2452 plasma concentration will be prepared for all cohorts, as appropriate.

10.1.2. Plasma Pharmacokinetic Parameters

The PK parameters of PB2452, ticagrelor, and TAM will be determined using noncompartmental methods using Phoenix WinNonlin Version 8.0 or higher or SAS® Version 9.4 or higher. For PK analysis, BLQ values will be treated as zero with the exception that a BLQ value between 2 quantifiable concentrations will be set as missing. If consecutive BLQ concentrations are followed by quantifiable concentrations in the terminal phase, those concentrations after BLQ concentrations will be treated as missing. Missing concentrations will be treated as missing from the PK parameter calculation

The following PK parameters, if data permit, will be calculated for total and unbound plasma PB2452 using actual sampling times.

PB2452 PK parameters:

Parameter	Description
C_{\max}	Observed maximum plasma concentration
T_{\max}	Time to reach the observed maximum plasma concentration
AUC_{0-t}	Area under the plasma concentration versus time curve (AUC) from time 0 to the time of last quantifiable concentration (C_{last}); calculated using the linear-up/ log-down trapezoidal rule
$AUC_{0-\infty}$	AUC from time 0 extrapolated to infinity, calculated as $AUC_{0-t} + C_{\text{last}}/\lambda_z$, where C_{last} is the last quantifiable plasma drug concentration and λ_z is the terminal phase rate constant.
AUC_{0-24}	AUC from time 0 to 24 hours post-dose; calculated using the linear-up/log-down trapezoidal rule
AUC_{0-48}	AUC from time 0 to 48 hours post-dose; calculated using the linear-up/ log-down trapezoidal rule
%AUC _{extrap}	Percentage of $AUC_{0-\infty}$ due to extrapolation from the time for the last quantifiable concentration to infinity, calculated as $(AUC_{0-\infty} - AUC_{0-t})/AUC_{0-\infty} * 100$

λz	Terminal phase rate constant, determined by linear regression of the terminal points of the log-linear plasma concentration-time curve. The λz will not be estimated if the terminal phase of the log-concentration-time profile does not exhibit a linear decline phase, or if the regression coefficient (Rsq) is less than 0.8.
Rsq	Regression coefficient for calculation of λz
$t_{1/2}$	Terminal elimination half-life, calculated as $t_{1/2} = \ln(2) / \lambda z$.
CL	Total body clearance, calculated as Dose/AUC _{0-inf}
Vd	Volume of distribution, calculated as CL/ λz .

The following PK parameters, as appropriate and when data permit, will be calculated for total and unbound ticagrelor and TAM using actual sampling times:

Ticagrelor/ TAM PK parameters:

Parameter	Description
C _{max}	Observed maximum plasma concentration
T _{max}	Time to reach the observed maximum plasma concentration
AUC _{0-t}	AUC from time 0 to the time of last quantifiable concentration (C _{last}); calculated using the linear-up/log-down trapezoidal rule
AUC _{0-inf}	AUC from time 0 extrapolated to infinity, calculated as AUC _{0-t} + C _{last} / λz , where C _{last} is the last quantifiable plasma drug concentration and λz is the terminal phase rate constant.
AUC ₀₋₂₄	AUC from time 0 to 24 hours post-dose; calculated using the linear-up/log-down trapezoidal rule
AUC ₀₋₄₈	AUC from time 0 to 48 hours post-dose; calculated using the linear-up/log-down trapezoidal rule
%AUCextrap	Percentage of AUC _{0-inf} due to extrapolation from the time for the last quantifiable concentration to infinity, calculated as (AUC _{0-inf} - AUC _{0-t}) / AUC _{0-inf} * 100
λz	Terminal phase rate constant, determined by linear regression of the terminal points of the log-linear plasma concentration-time curve. The λz will not be estimated if the terminal phase of the log-concentration-time profile does not exhibit a linear decline phase, or if the regression coefficient (Rsq) is less than 0.8.
Rsq	Regression coefficient for calculation of λz
$t_{1/2}$	Terminal elimination half-life, calculated as $t_{1/2} = \ln(2) / \lambda z$.

Additional PK parameters may be calculated, as necessary. Pharmacokinetic parameters will be listed by subject and summarized for each dose level using descriptive statistics (number of subjects, mean, SD, CV, median, minimum, and maximum), with the exception of %AUCextrap, λz and Rsq, which will be listed only. Geometric means will be reported for AUCs and C_{max}.

